6.2 Dose-Modification Guidelines

6.2.1 Recommended Ixazomib Criteria for Beginning or Delaying a Subsequent Treatment Cycle & Dose Modifications for Treatment Associated Toxicity

Treatment with Ixazomib will use a cycle length of 28 days. The next cycle should begin as soon as possible, but no later than 14 days after the end of the previous cycle. Unavoidable deviations from this schedule will be permissible with prior approval by the Principal Investigator or Study Chair. For a new cycle of treatment to begin, the patient must meet the following criteria within 3 days prior to drug being dispensed:

- ANC must be $\geq 1,000/\text{mm}^3$.

- Platelet count must be $\geq 75,000/\text{mm}^3$.
- All other non-hematologic toxicity (except for alopecia) must have resolved to \leq Grade 1 or to the patient's baseline condition

These laboratory tests should be performed and reviewed at the study site.

If the patient fails to meet the above-cited criteria for initiation of the next cycle of treatment, dosing should be delayed for 1 week. At the end of that time, the patient should be re-evaluated to determine whether the criteria have been met. If the patient continues to fail to meet the above-cited criteria, delay therapy and continue to re-evaluate. The maximum delay before treatment should be discontinued will be 3 weeks or at the discretion of the Principal Investigator.

Ixazomib dose adjustments are described in table 6-1. For dosing recommendations for hematologic toxicities and non-hematologic toxicities, see Table 6-2 and Table 6-3 respectively.

Table 6-1 Ixazomib Dose Adjustments

Dose Level	Dose (mg)
Starting Dose	4.0 mg
-1	3.0 mg
-2	2.3 mg
-3	Discontinue

Table 6-2 Ixazomib Dose Adjustments for Hematologic Toxicities

Criteria	Action
Within-Cycle Dose Modifications	

 • If platelet count $\leq 30 \times 10^9/L$ or ANC $\leq 0.50 \times 10^9/L$ on a Ixazomib dosing day (other than Day 1) 	
 • Ixazomib dose should be withheld. • Complete blood count (CBC) with differential should be repeated until the ANC and/or platelet counts have exceeded the prespecified values (see Section 6.2.1) • Upon recovery, Ixazomib may be reinitiated with 1 dose level reduction.
Dose Modifications for Subsequent Treatment Cycles	

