Other Grade 3 non-hematologic toxicity judged to be related to study drug	
 • Hold study drug until resolution to Grade < 1 or baseline 	Symptomatic recommendations noted in Section 6.6
If recovered to $<$ Grade 1 or baseline within 4 weeks	Reduce study drug 1 to next lower dose upon return to $<$ Grade 1 or baseline	

Table 6-3 Ixazomib Treatment Modification (Delays, Reductions, and Discontinuations) Due to Adverse Events (Non-Hematologic Toxicities)

Adverse Event (Severity)	Action on Study Drug	Further Considerations
If not recovered to < Grade 1 or baseline within 4 weeks	
 Reduce study drug 1 to next lower dose upon return to < Grade 1 or baseline 	
Subsequent recurrence	
 Follow above management guidelines 	Monitor closely, take appropriate medical precautions, and provide appropriate symptomatic care
Grade 3 that does not recover to < Grade 1 or baseline within 4 weeks	
 Reduce study drug to next lower dose 	
Grade 4 nonhematologic toxicities judged to be related to study drug	Consider permanently discontinuing study drug	Exceptions are cases in which the investigator determines the patient is obtaining a clinical benefit

Once Ixazomib is reduced for any toxicity, the dose may not be re-escalated.

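### The Grade 3 non-hematologic rows of Table 6-3 contradict each other and Section 6.2.1, so sites have no single instruction for an event not recovered at 4 weeks

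*Combined protocol and SAP*

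**What the plan says.** Table 6-3 (Section 6.2.1) deals with related Grade 3 non-hematologic toxicity, other than neuropathy, in this order:

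- Opening row: "Hold study drug until resolution to Grade < 1 or baseline".
- Recovered within 4 weeks: "Reduce study drug 1 to next lower dose upon return to $<$ Grade 1 or baseline".
- Not recovered, "If not recovered to < Grade 1 or baseline within 4 weeks": the same action as the row before, including the wait for recovery.
- Recurrence: "Follow above management guidelines".
- Last Grade 3 row, "Grade 3 that does not recover to < Grade 1 or baseline within 4 weeks": the whole action is "Reduce study drug to next lower dose".

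The text of Section 6.2.1 sets a separate test: "For a new cycle of treatment to begin, the patient must meet the following criteria within 3 days prior to drug being dispensed". One criterion is "All other non-hematologic toxicity (except for alopecia) must have resolved to" Grade 1 or lower, or to the patient's baseline. If the test is failed, dosing is delayed and the patient re-evaluated. Treatment is to stop after a maximum delay of 3 weeks, or at the Principal Investigator's discretion. The same section wants the next cycle to start within 14 days of the end of the previous one, with approved deviations allowed. Table 6-2 repeats the hold for non-hematologic toxicity above Grade 1 and the 3-week limit. Section 6.11 lists unresolved toxicity as a reason to stop ixazomib.

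**The concern.** Two rows of one table describe a Grade 3 event still unrecovered at 4 weeks. One makes the lower dose wait for recovery; the other does not. Elsewhere the protocol states the recovery condition when it wants one: the neuropathy row that lowers the dose does so, and so does Table 6-2. Its absence from the last Grade 3 row could therefore be read as deliberate.

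This bears on patient safety, because the rows give different answers on whether a patient with unresolved related toxicity may take the next dose. It also bears on exposure. A reduction cannot be undone, since the note after Table 6-3 rules out re-escalation. In a multi-center trial, delivered dose would depend partly on which row a site follows.

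**Working it through.** The plan gives no statistical figure here, so the check sets the passages side by side and then looks at timing.

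**1. The instructions at 4 weeks**

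| Place | State described | Action | Recovery required first? |
|---|---|---|---|
| Table 6-3, opening Grade 3 row | Related Grade 3 event | Hold | Yes, below Grade 1 or baseline |
| Table 6-3, recovered row | Recovered within 4 weeks | One level down | Yes, below Grade 1 or baseline |
| Table 6-3, not-recovered row | Not recovered within 4 weeks | One level down | Yes, below Grade 1 or baseline |
| Table 6-3, last Grade 3 row | Not recovered within 4 weeks | One level down | Not stated |
| Section 6.2.1 text | New cycle due | Delay; stop after 3 weeks or at Principal Investigator discretion | Yes, Grade 1 or lower, or baseline |
| Table 6-2 | Non-hematologic toxicity above Grade 1 or not at baseline | Hold, then one level down; same 3-week limit | Yes, by the Section 6.2 criteria |

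The third and fourth rows state the same condition and differ on recovery. The second and third state opposite conditions and carry the same action, so the 4-week split changes nothing between them.

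**2. Does the last row cover only recurrences?** It follows the recurrence row, so it might. But the recurrence row points back to the guidance above it, which requires recovery. A recurrence-only reading removes the duplicate and leaves a conflict.

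**3. Where the 4-week point falls.** Inputs: a 28-day cycle (Section 6.2.1), so the next cycle is due on Day 29; doses on Days 1, 8 and 15 (Section 6.1). Assumption: the 4 weeks run from onset on cycle day d. Then

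4-week point = d + 28; days past the due date = (d + 28) − 29 = d − 1.

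| Onset day d | 4-week point | Days past Day 29 |
|---|---|---|
| 1 | 29 | 0 |
| 8 | 36 | 7 |
| 15 | 43 | 14 |
| 22 | 50 | 21 |
| 28 | 56 | 27 |

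For every onset day from 1 to 28 the point is Day 29 or later. On the normal schedule the next dose then opens a new cycle and must pass the Section 6.2.1 test. Counting the 4 weeks from a later start of the hold only moves the point later.

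**4. Time limits.** For onset after Day 15, the 4-week point lies beyond the 14-day limit. For onset after Day 22, it lies beyond the 3-week maximum delay, so Section 6.2.1 may already call for discontinuation before the Table 6-3 rows apply. Both boundaries count from Day 29; counting from Day 28 moves each one day earlier.

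**5. Thresholds.** A patient at Grade 1 with a baseline of zero passes the Section 6.2.1 test but is unrecovered under these Table 6-3 rows. The neuropathy rows of the same table use Grade 1 or lower.

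**The case against.** The best defence is that the harm is already blocked. The Section 6.2.1 test is mandatory, and step 3 shows that a dose under the last Grade 3 row would meet it on the normal schedule. Principal Investigator discretion is attached to the maximum delay, and approved deviations to the schedule; neither is written as a waiver of the recovery criterion. The last row also names a dose level without saying to resume, so it may only set the level for when dosing restarts under the opening hold.

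Much of this stands. A reader might infer that the protocol tells sites to dose a patient who still has Grade 3 toxicity. The documents do not support that. It requires reading the last row alone, against both the hold and the Section 6.2.1 test. An event not yet below Grade 1 may also have improved to Grade 1 or 2, so the residual toxicity need not be Grade 3.

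The defence does not remove the contradiction. It works by choosing one passage over another, and nothing in the protocol says which prevails. The last row is the more specific text for this state.

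It is also fair that the primary endpoint (Section 3.1) counts new systemic immune suppression, recurrent malignancy or death, and not dose level. Any effect on the primary analysis is indirect, through exposure.

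**Conclusion.** The contradiction is real and should be fixed. Table 6-3 gives two answers for a Grade 3 event not recovered at 4 weeks, its 4-week split has no effect, and its threshold and time limit do not match Section 6.2.1. The same patient could be held, reduced or discontinued according to the passage a site follows. From the 4.0 mg starting dose in Table 6-1, that means no drug until recovery, 3.0 mg (3.0/4.0 = 75%), or an end to treatment. The fault is conflicting instructions, not a clear order to dose.

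The number of patients affected cannot be derived. A reader might apply the 17% rate of drug-related Grade 3 or higher diarrhea in the weekly single-agent study (Table 1-4) to 50 patients, giving 0.17 × 50 = 8.5, and take a share of that. The rate includes Grade 4 events, which have their own row in Table 6-3. It comes from a myeloma study with doses up to 3.95 mg/m² (Table 1-1), whereas 4.0 mg here corresponds to about 2.23 mg/m². The documents give no share unrecovered at 4 weeks.

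The timing result assumes 28-day cycles run as scheduled. The threshold mismatch assumes that the strict sign in the Grade 3 rows is what the table prints; check it against the source file.

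**What to change.** The sponsor should reconcile the Grade 3 rows of Table 6-3 with each other and with the criteria, thresholds and time limits in Section 6.2.1 and Table 6-2. Specifically:

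- Keep one row for an event not recovered at 4 weeks, and say in it whether recovery is required before any further dose.
- State how the action differs, if at all, from that for recovery within 4 weeks.
- Clarify whether the last Grade 3 row applies only to recurrences.
- Use one recovery threshold, or explain why two are needed.
- State how the 4-week, 3-week and 14-day limits fit together, and which passage prevails in a conflict.

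The clinical rule is for the sponsor to set. The cost is rewording a few table rows and a note to sites; sample size and analysis do not change.

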6.2.2 Recommended Dose Modifications for <other drug(s)> Treatment Associated Toxicity

6.3 Excluded Concomitant Medications

The following medications are prohibited during the study:

Systemic treatment with any of the following metabolizing enzyme inhibitors is not permitted during this study. A Drug-Drug Interaction (DDI) with a strong inhibitor would increase MLN2238 exposure.

- Strong inhibitors of CYP1A2: fluvoxamine, enoxacin, ciprofloxacin
- Strong inhibitors of CYP3A: clarithromycin, telithromycin, itraconazole, voriconazole, ketoconazole, nefazodone, and posaconazole

Systemic treatment with any of the following metabolizing enzyme inducers should be avoided A DDI with a strong inducer would decrease MLN2238 exposure.

- Strong CYP3A inducers: rifampin, rifapentine, rifabutin, carbamazepine, phenytoin, and phenobarbital
- The dietary supplements St John's wort and Ginkgo biloba .

6.4 Permitted Concomitant Medications and Procedures

The following medications and procedures are permitted during the study:

- Antiemetics, including 5-HT3 serotonin receptor antagonists, may be used at the discretion of the investigator.
- Loperamide or other antidiarrheal should be used for symptomatic diarrhea at discretion of the investigator. The dose and regimen will be according to institutional guidelines.
- Growth factors (eg, granulocyte colony stimulating factor [G-CSF], granulocyte macrophage-colony stimulating factor [GM-CSF], recombinant erythropoietin) are permitted. Their use should follow published guidelines and/or institutional practice.
- Patients should be transfused with red cells and platelets as clinically indicated and according to institutional guidelines.
- Antiviral therapy such as acyclovir may be administered if medically appropriate.

6.5 Precautions and Restrictions

Fluid deficits should be corrected before and throughout treatment.

NSAIDs should be avoided in patients with impaired renal function given reported NSAID-induced renal failure in patients with decreased renal function.

Pregnancy

It is not known what effects Ixazomib has on human pregnancy or development of the embryo or fetus. Female patients participating in this study should avoid becoming pregnant, and male patients should avoid impregnating a female partner. Non-sterilized

female patients of reproductive age group and male patients should use effective methods of contraception through defined periods during and after study treatment as specified below.

Female patients must meet 1 of the following criteria:

- Postmenopausal for at least 1 year before the screening visit, OR
- Surgically sterile, OR
- If they are of childbearing potential, agree to practice 2 effective methods of contraception, at the same time, from the time of signing the informed consent form through 90 days after the last dose of study drug, OR
- Agree to practice true abstinence or exclusively non-heterosexual activity when this is in line with the preferred and usual lifestyle of the subject. (Periodic abstinence [eg, calendar, ovulation, symptothermal, post-ovulation methods] and withdrawal are not acceptable methods of contraception.)

Male patients, even if surgically sterilized (ie, status postvasectomy), must agree to 1 of the following:

- Agree to practice two effective contraception measures during the entire study treatment period and through 90 days after the last dose of study drug, OR
- Agree to practice true abstinence or exclusively non-heterosexual activity when this is in line with the preferred and usual lifestyle of the subject. (Periodic abstinence [eg, calendar, ovulation, symptothermal, post-ovulation methods] and withdrawal are not acceptable methods of contraception.)

6.6 Management of Clinical Events

Adverse drug reactions such as thrombocytopenia, diarrhea, fatigue, nausea, vomiting, and rash have been associated with Ixazomib treatment. Management guidelines regarding these events are outlined below. Further details of management of Ixazomib AEs are described in Section 6 of the Ixazomib IB.

Prophylaxis Against Risk of Infection

Infection prophylaxis should follow institutional standards.

Nausea and/or Vomiting

Standard anti-emetics may be used for prophylaxis and treatment of nausea or vomiting.

Diarrhea

Diarrhea should be managed according to clinical practice, including the administration of antidiarrheals. Fluid intake should be maintained to avoid dehydration.

Erythematous Rash With or Without Pruritus

Rash should be managed symptomatically according to standard medical practice, including supportive care, oral or topical steroids, and/or anti-histamines.

Thrombocytopenia

Blood counts should be monitored regularly as outlined in the protocol with additional testing obtained according to standard clinical practice. Ixazomib administration should be modified as noted as per dose modification recommendations in Table 6-2 when thrombocytopenia occurs. Therapy can be reinitiated at a reduced level upon recovery of platelet counts.

Neutropenia

Blood counts should be monitored regularly as outlined in the protocol with additional testing obtained according to standard clinical practice. Ixazomib administration should be modified when neutropenia occurs, as noted in the dose modification recommendations in Table 6-2. Therapy can be reinitiated at a reduced level upon recovery of absolute neutrophil counts. The use of growth factors (e.g. G-CSF) is permitted.

Fluid Deficits

Fluid deficits should be corrected before initiation of study drug and during treatment and as needed during therapy.

Hypotension

Blood pressure should be closely monitored while the patient is on study treatment and fluid deficit should be corrected as needed.

Posterior Reversible Encephalopathy Syndrome

One case of posterior reversible encephalopathy syndrome (PRES) has been reported with Ixazomib. While this case ultimately resolved, PRES has also been reported rarely with another proteasome inhibitor, VELCADE. PRES is characterized by headache, seizures and visual loss, as well as abrupt increase in blood pressure. Prompt diagnosis and initiation of antihypertensive and anticonvulsant therapy are important to prevent irreversible end-organ damage.

Transverse Myelitis

Transverse myelitis has also been reported with Ixazomib. It is not known if Ixazomib causes transverse myelitis; however, because it happened to a patient receiving Ixazomib, the possibility that Ixazomib may have contributed to transverse myelitis cannot be excluded.

6.7 Preparation, Reconstitution, and Dispensing

Ixazomib is an anticancer drug and as with other potentially toxic compounds caution should be exercised when handling Ixazomib capsules.

Millennium will ship study medication directly to participating sites, and notify [name] when each shipment is made. See the Manual of Operations for more details.

6.8 Packaging and Labeling

The study drug Ixazomib capsules will be provided by Millennium. The study drug will be labeled and handled as open-label material, and packaging labels will fulfill all requirements specified by governing regulations.

Ixazomib capsules should be stored unopened at 2°C to 8°C (36°F-46°F). The capsules are individually packaged in cold form foil-foil blisters in a child-resistant package. The 2.3-, 3.0-, and 4.0 mg capsules are supplied as a 1 x 3 blister card in a child-resistant cardboard wallet.

6.9 Storage, Handling, and Accountability

Upon receipt at the investigative site, Ixazomib should remain in the blister and carton provided until use or until drug is dispensed. The container should be stored at the

investigative site refrigerated (36°F to 46°F, 2°C to 8°C). Ensure that the drug is used before the retest expiry date provided by Millennium. Expiry extensions will be communicated accordingly with updated documentation to support the extended shelf life.

Ixazomib capsules dispensed to the patient for take-home dosing should remain in the blister packaging and refrigerated as noted above until the point of use. The investigative site is responsible for providing the medication to the patient in the correct daily dose configurations. Comprehensive instructions should be provided to the patient in order to ensure compliance with dosing procedures. Patients who are receiving take-home medication should be given only 1 cycle of medication at a time. Patients should be instructed to store the medication refrigerated (36°F to 46°F, 2°C to 8°C) for the duration of each cycle. Patients should be instructed to return their empty blister packs to the investigative site, rather than discarding them. Reconciliation will occur accordingly when the patient returns for their next cycle of take-home medication. Any extreme in temperature should be reported as an excursion and should be dealt with on a case-by-case basis.

Because Ixazomib is an investigational agent, it should be handled with due care. Patients should be instructed not to chew, break, or open capsules. In case of contact with broken capsules, raising dust should be avoided during the clean-up operation. The product may be harmful by inhalation, ingestion, or skin absorption. Gloves and protective clothing should be worn during cleanup and return of broken capsules and powder to minimize skin contact.

The area should be ventilated and the site washed with soap and water after material pick-up is complete. The material should be disposed of as hazardous medical waste in compliance with federal, state, and local regulations.

In case of contact with the powder (eg, from a broken capsule), skin should be washed immediately with soap and copious amounts of water for at least 15 minutes. In case of contact with the eyes, copious amounts of water should be used to flush the eyes for at least 15 minutes. Medical personnel should be notified. Patients are to be instructed on proper storage, accountability, and administration of Ixazomib, including that Ixazomib is to be taken as intact capsules.

6.10 Study Compliance

Study drug will be administered or dispensed only to eligible patients under the supervision of the investigator or identified sub-investigator(s). The appropriate study personnel will maintain records of study drug receipt and dispensing.

6.11 Discontinuation of Ixazomib therapy

Patients will be informed that they have the right to withdraw from the study at any time for any reason, without prejudice to their medical care. In the following circumstances, Ixazomib therapy will be discontinued, however active study follow up will continue until study-defined treatment failure occurs (i.e. death, relapse, or addition of a new systemic immune suppressive therapy). The End of Treatment visit should occur as soon as possible after ixazomib is stopped.:

- The treating clinician determines that the patient has responded to therapy and does not require any additional Ixazomib therapy
- Ixazomib therapy is discontinued due to unresolved toxicity
- Ixazomib therapy is discontinued due to patient non-adherence to therapy

6.12 Termination of study participation

The following conditions require discontinuation of Ixazomib therapy and/or termination of active study follow up:

- Patient decision to withdraw from the study
 - o At the time of withdrawal, all study procedures outlined for the End of Treatment visit should be completed. The primary reason for patient's withdrawal from the study should be recorded in the source documents and CRF.

- Ixazomib therapy is discontinued due to the addition of (or planned addition of) another line of systemic immune suppressive therapy
 - o The End of Treatment visit should be completed as close as possible to the date that ixazomib is stopped. The date that the new systemic treatment is started should be recorded.
- The patient has relapse of their hematologic disorder or malignancy after transplant
 - o The End of Treatment visit should be completed if possible.
- Death
- Completion of all study follow up

7. STATISTICAL AND QUANTITATIVE ANALYSES

7.1 Statistical Methods

7.1.1 Determination of Sample Size and planned methods of analysis

The primary endpoint is overall treatment failure at 6 months from study enrollment. Treatment failure represents the composite including addition of new line of systemic immune suppressive therapy beyond Ixazomib (objective signal of failure to control GVHD with Ixazomib), non-relapse death, and primary malignancy relapse.²⁹ The historical benchmark for this outcome based on this analysis of 312 chronic GVHD patients is a 6 month treatment failure rate of 44%. With 50 patients, the standard error of the estimated failure rate will be approximately 7 percentage points.

With 50 subjects and a 1-sided alpha of 0.1, there will be 82% power to detect a 15 percentage point reduction in the 6 month treatment failure rate, relative to the reference rate of 44%, based on an exact binomial calculation using that option in nQuery. This reduction is deemed feasible based on the following: The major contribution to the observed treatment failure rate was 34% requiring additional immune suppressive therapy beyond second-line

therapy. Assuming effective therapy with ongoing Ixazomib over the treatment period could reduce this risk by 50% (i.e. to 17%) with little or no increased risk for relapse (3% in this published analysis) or non-relapse death (7% in this analysis), the overall improvement in the 6 month treatment failure rate could be 15%. Patients who are lost to follow up or otherwise not evaluable will not be replaced.

Although the overall 6 month failure rate in the historical benchmark study was 44%, this varied from 33% to 41% to 56% for patients that were classified as low, intermediate and high risk, respectively. Thus the relative proportions of patients in the different risk categories will need to be considered in order to interpret the possible benefit of Ixazomib therapy.

Time-to-event endpoints will be evaluated using Kaplan-Meier and cumulative incidence methods; response endpoints will be evaluated as proportions; patient-reported outcomes will be summarized as frequencies, or with mean and SD, as appropriate. The only comparative analysis will involve the biologic endpoints, where responders at 3 and 6 months will be compared to nonresponders, based on baseline values and on changes from baseline. This will involve standard parametric or non-parametric methods, depending on the observed distribution of these endpoints.

In the analysis of secondary objectives, we will study the 3 and 6 month overall (complete + partial) response and complete response rates, other efficacy measures listed above, patient reported outcomes, and biologic outcome measures. We will study association between biologic outcome measures and clinical parameters (response, treatment failure, mortality).

